7.3 CAPSCAN DEVICE USE PHASE

- The CapScan Devices are provided in a sealed containers.
- The subject uses a device retrieval wand to look for and collect the expelled devices in the stool after all bowel movements for up to 8 days after swallowing a CapScan Device.
- The end of the study is defined when the last swallowed CapScan Device is retrieved from the stool. The study representative will collect all of the retrieved samples and the Daily Diaries from home of the subject.

7.3 PROTOCOL AMENDMENTS, REVISION AND/OR DEVIATIONS

The protocol must be read thoroughly and its instructions and guidelines must be followed exactly. Any changes in the protocol will require a formal amendment document. Such amendments will be agreed upon and approved in writing by the PI and Envivo Bio Inc. All modifications and revisions will be noted and summarized on page 1 of this protocol document. The Institutional Review Board (IRB) will be notified of all significant amendments to the protocol. Significant amendments to the protocol that may increase risk to the subject, and/or that may adversely affect the rights of the subject or the validity of the investigation will not be implemented until IRB committee written approval has been received.

With the exception of emergency situations, no significant changes or deviations in the conduct of this protocol will be permitted without the prior documented approval of Envivo Bio Inc. The IRB that granted the original approval for the study must be notified of all material changes in the protocol, and must provide a written approval of any significant change or significant deviation that may increase risk to the subject, and/or that may adversely affect the rights of the subject or the validity of the investigation.

In the event of an emergency, the PI will institute any medical procedures deemed appropriate. However, all such procedures must be promptly reported to Envivo Bio Inc. and the IRB.

7.4 MANUFACTURING AND SUPPLY OF INVESTIGATIONAL DEVICE

Envivo Bio Inc. will supply the CapScan Devices to the investigational site or subjects in appropriately labeled packaging.

The CapScan Device will be manufactured and packaged by Envivo Bio Inc. and/or its designated sub-contractors in compliance with the relevant principles and guidelines applicable to investigational medical devices.

7.5 STORAGE AND ACCOUNTABILITY OF INVESTIGATIONAL DEVICE

The CapScan Devices will be kept in a secure, limited-access, room temperature storage area at the investigational site or dispensed directly to the subjects by the Sponsor. Only authorized personnel will have access to the study devices. Complete traceability records will be kept of all devices during the study. Specifically, a study accountability log will be completed to maintain accurate records of all CapScan Device inventory.

7.6 RETURN OF INVESTIGATIONAL DEVICE

Government regulations require that all investigational product materials not used in clinical trials be returned to the Sponsor at the completion of the study. The monitor will be responsible for the accountability of the returned of used and unused investigational devices.

7.7 CONTRA-INDICATION

No contraindications related to the CapScan Device are currently known.

8. STUDY ASSESSMENT METHODS

8.1 SAFETY ASSESSMENTS

8.1.1 Adverse Events

Adverse Events (AE's) reported by subjects or observed by the PI or PI designee will be documented in the source document, assessed by the PI and will be individually listed on an adverse event page in the CRF. Recording of AE's will begin immediately after the signing of the informed consent document and continue until the subject dies, withdraws consent, or 48 hours after the End of Study (EOS), regardless of the relationship of the AE to the CapScan Device. If a subject complains of any AE within 5 days of the EOS that the PI deems definitely, probably, or possibly related to the device, the event will be documented and followed until all parameters

(including laboratory) have returned to normal, stabilized, or are otherwise explained. The subject will be evaluated by the PI within 72 hours of the PI becoming aware of the AE.

Information to be collected includes type of event, date of onset, date of resolution, investigator-specified assessment of severity and relationship to device, seriousness, as well as any action taken.

All conditions present before the Screening Visit will be documented as medical history.

Specific procedures for recording and reporting serious adverse events are described in section 10.5.

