If a subject complains of any Adverse Event (AE) within 5 days of the End of Study that the investigator deems related to the device, the event will be documented and the subject will be evaluated by the principal investigator or sub investigator within 72 hours of either investigator becoming aware of the AE.

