10.5 REPORTING OF ADVERSE EVENTS

Any Serious adverse event (SAE) and device respectively procedure-related (Relatedness: definite, probably and possibly) Adverse Effect (SADE), must be fully recorded utilizing the sponsor provided SAE form and reported in writing by the Principal Investigator to Envivo Bio Inc. within 24 hours of becoming aware of the event.

The PI will complete the Serious Adverse Event Form and email a scanned copy to Envivo Bio Inc. sponsor and the medical monitor contacts as follows:

Additional information (follow-up) about any SAE or SADE unavailable at the initial reporting should be forwarded by the site to the Envivo Bio Inc. as soon as they become available (such as hospital discharge).

Envivo Bio Inc. will review and assess with the PI any SAE's and any serious device/procedurerelated adverse effects. Envivo Bio Inc. ensures that reporting requirements according to the local regulations are fulfilled.

All SAE's which are considered as device- or procedure-related will be reported to IRB by the PI.

Subjects who have had an SAE during the Treatment Phase must be followed clinically until all parameters (including laboratory) have returned to normal, have stabilized, or are otherwise explained. The study period for the purpose of SAE reporting is defined as the period from time of informed consent until 14 days after the End of Study.

If the investigator detects a SAE in a trial subject after the end of the period of observation, and considers the event possibly related to the prior trial, he should contact the sponsor to determine how the AE should be documented and reported.

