11. STATISTICAL ANALYSIS PLAN

Due to the small sample size and the study objectives, the statistics will be mainly descriptive by nature. For categorical variables, summary tables will be provided giving sample size, absolute

and relative frequency. For continuous variables summary tables will be provided giving sample size, arithmetic mean, standard deviation, standard error of the mean (SEM), median, minimum and maximum, percentiles and 95% CI (Confidence Interval) for means of variables.

Tables of descriptive statistics will be presented for the following variables:

- Adverse events and device-related adverse events in the clinical documentation.
- Effectiveness of the CapScan Device in collecting measurable quantities of metabolic breakdown products of sulfasalazine and for the identification of microbial enzyme genes.

All safety data will be summarized across the cohort with descriptive statistics. The incidence of adverse events during the treatment period will be summarized.

All adverse events will be classified by System Organ Class and preferred term according to the Medical Dictionary for Regulatory Activities (MedDRA). The latest version available at the time of coding will be used throughout the study.

All adverse events will be listed together with information on onset, duration, frequency, severity, seriousness, relationship to the investigational product, outcome and action taken. Frequency tables for severity and relationship to the Envivo Bio Device device will be provided by System Organ Class and preferred term.

The main analysis will not include events which started before the first use of CapScan Device number 1; only treatment emergent adverse events will be included in the summary tables.

VAS scores and changes from baseline will be presented by appropriate summary tables. Changes from baseline will be analyzed using Paired T-test or Signed rank test for two means (paired observations, or as appropriate).

Any deviation from the statistical analysis plan will be recorded together with an explanation of the deviation.

The data will be analyzed using standard statistical software (e.g., SAS [Cary, NC] or R [Vienna, Austria]).

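### Non-serious adverse events are recorded for 48 hours or 5 days after End of Study depending on judged cause, and Section 11 sets no common end for the tables that report cause

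*Combined protocol and SAP*

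**What the plan says.** Three follow-up windows run from End of Study, which Section 5 ties to retrieval of the last device or to the investigator's determination that none remains in the body.

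- **All AEs (Section 8.1.1):** recording starts at consent and, barring death or withdrawal of consent, runs until "48 hours after the End of Study (EOS), regardless of the relationship of the AE to the CapScan Device".
- **Device-related AEs (Section 8.1.1):** an AE is also documented and followed if the subject complains of it "within 5 days of the EOS that the PI deems definitely, probably, or possibly related to the device". Section 2.2 has the same rule ("within 5 days of the End of Study that the investigator deems related to the device, the event will be documented"), and so does the synopsis.
- **Serious AEs (Section 10.5):** the reporting period is the "period from time of informed consent until 14 days after the End of Study", with no condition on cause. Section 10.6 puts each serious event on the ordinary AE page as well.

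Section 11 then promises: "Frequency tables for severity and relationship to the Envivo Bio Device device will be provided by System Organ Class and preferred term". Its lower limit is explicit: "The main analysis will not include events which started before the first use of CapScan Device number 1". It gives no upper limit for treatment-emergent events. It also summarises incidence over a treatment period that is not defined.

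**The concern.** From 48 hours to 5 days after End of Study, the plan selects non-serious events on the variable it later tabulates. An event on the fourth day after End of Study is documented if the investigator relates it to the device. The same event judged unrelated has no instruction in Section 8.1.1 to be recorded. If the late events reach the tables, related and unrelated events have been counted over different lengths of time.

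A second problem needs no assumption about rates. Table 4 in Section 10.3 judges relationship to the device only, so a reaction explained wholly by sulfasalazine counts as unrelated. The recording window is set by device retrieval and not by the dose. A late, non-serious, drug-attributed event therefore lies outside the Section 8.1.1 rule. Section 12 says the study is meant to demonstrate safety, and these tables are its safety result.

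**Working it through.** The plan states no AE rate and no device-related share, so there is no figure to reproduce. The check is person-time arithmetic.

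**Inputs from the protocol.** E is the number of days from first device use to End of Study, with Day 1 counted as one day.
- E = 3: last device retrieved on Day 3.
- E = 8: the end of the first retrieval period (Section 5).
- E = 25: a repeat cycle that starts on Day 19 and runs the seven days matching Days 2 to 8 (19 + 6 = 25).
- E = 5 is added as an intermediate value.
- Windows for non-serious AEs: E + 2 days if unrelated, E + 5 days if related.

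**Assumptions, not in the protocol.** p is the true device-related share of the on-study AE rate. f is the rate of related AEs after End of Study relative to the on-study rate. Unrelated AEs occur at a constant rate.

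**Formulas.**
- Late related events tabulated: p(E+5f) / [p(E+5f) + (1−p)(E+2)]
- Common 48-hour cut: p(E+2f) / [p(E+2f) + (1−p)(E+2)]
- Common 5-day window: p(E+5f) / [p(E+5f) + (1−p)(E+5)]

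**Step 1: equal constant rates (f = 1, p = 0.5).** Either common window returns 50.0%.

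| E | Related, days | Unrelated, days | Ratio | Share if late events are tabulated |
|---|---|---|---|---|
| 3 | 8 | 5 | 1.60 | 8/13 = 61.5% |
| 5 | 10 | 7 | 1.43 | 10/17 = 58.8% |
| 8 | 13 | 10 | 1.30 | 13/23 = 56.5% |
| 25 | 30 | 27 | 1.11 | 30/57 = 52.6% |

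At E = 8, a true 20% share becomes 24.5% and a true 80% share becomes 83.9%.

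**Step 2: related events become rarer once the devices are out (E = 8, p = 0.5).**

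| f | Late events tabulated | Common 48 hours | Common 5 days |
|---|---|---|---|
| 1 | 13/23 = 56.5% | 10/20 = 50.0% | 13/26 = 50.0% |
| 0.25 | 9.25/19.25 = 48.1% | 8.5/18.5 = 45.9% | 9.25/22.25 = 41.6% |
| 0 | 8/18 = 44.4% | 8/18 = 44.4% | 8/21 = 38.1% |

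The excess over a common 48-hour cut is 6.5 points, about 2 points and zero. At E = 3 with f = 0.25 it is about 5 points (4.25/9.25 = 45.9% against 3.5/8.5 = 41.2%). It cannot be negative for non-serious AEs, because the late rule adds 3f days of related events and no unrelated ones.

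**Step 3: serious events.** Section 10.5 covers these to 14 days whatever the cause, so the asymmetry concerns non-serious AEs only. A late unrelated serious event that entered the table would lower the related share.

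**Step 4: drug-attributed events.** The dose is on Day 2. If End of Study falls on Day 3, general recording closes on Day 5, three days after the dose. For comparison, Section 5 allows no repeat dose before Day 12, so that the drug can clear. Section 2.4.1 has subjects report any side effect, and Section 10.6 documents every AE reported or detected, with no time limit. Section 8.1.1 has a limit. The sections do not say which governs.

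**The case against.** A reader might infer that the tables do count the two classes over different windows, and that the related share will be reported as 57% or 62% when it is truly 50%. The documents do not support that.

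- Nothing states that events from 48 hours to 5 days after End of Study enter the tables. If the undefined treatment period ends at End of Study or 48 hours later, the distortion is zero. This stands.
- The 57% and 62% figures need the related rate to continue unchanged after the devices have left the body. The tabulated share exceeds p only if E + 5f > E + 2, that is f > 0.4. This stands.
- A repeat cycle dilutes the effect: at E = 25 the share is 52.6% even with f = 1. This stands.
- The study has up to 10 subjects, is descriptive, and rests no inference on the share. All AEs are to be listed with onset and relationship, so a recorded late event can be re-cut. That is true of recorded events, but no re-cut recovers unrelated events that were never recorded.
- A reader might also infer that every late drug reaction is lost. That goes too far. The *possibly* category in Table 4 admits events that either the device or another agent may explain, and Section 10.6 points towards recording. Only events attributed purely to the drug are exposed, and for those the sections conflict.

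These points limit the size. They do not remove a recording rule that depends on causality and is stated in three places.

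**Conclusion.** The point holds as a conditional one. Non-serious AEs are recorded over windows that differ by judged cause, and Section 11 leaves open whether the late ones are tabulated. If they are, the device-related share can be overstated: a true 50% becomes about 53% to 62% for End of Study between Day 25 and Day 3, assuming equal constant rates that continue after the devices are out. Against a common 48-hour cut, the excess shrinks towards zero as related events cease, and it is zero if the tables stop by then. An inflated share is therefore possible but not demonstrated.

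The gap for late non-serious events attributed only to sulfasalazine does not depend on these rates. It rests on Section 8.1.1 and Table 4 read together, and on their conflict with Sections 2.4.1 and 10.6.

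**What to change.** **Preferred.** In Section 8.1.1, record all AEs regardless of relationship through 5 days after End of Study. In Section 11, make that the common end of the treatment-emergent period, defined by onset date, for the incidence and relationship tables. List serious events with later onset separately. This addresses both problems. The cost is three more days of AE recording per subject, at most 30 subject-days for 10 subjects (replacements aside), with no new procedure.

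**Alternative.** Add one sentence to Section 11 that restricts the tables to onset within 48 hours of End of Study for all causes, and list later device-related AEs and serious AEs separately, outside the percentages. This equalises the tables at almost no cost but leaves late drug-attributed non-serious AEs uncaptured.

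Under either option, define the treatment period in Section 11 and reconcile Sections 8.1.1, 10.5, 10.6 and 11, together with the 5-day sentences in Section 2.2 and the synopsis.

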8.1.2 General Health Assessment

General health of the subject will be assessed at the Screening Visit utilizing the American Society of Anesthesiologists (ASA) Physical Status Classification System. Only subjects with an ASA classification of 1 and 2 will be eligible to participate in the trial.

- ASA Physical Status **1** A normal healthy patient
- ASA Physical Status **2** A patient with mild systemic disease
- ASA Physical Status **3** A patient with severe systemic disease
- ASA Physical Status 4 A patient with severe systemic disease that is a constant threat to life
- ASA Physical Status 5 A moribund patient who is not expected to survive without the operation
- ASA Physical Status 6 A declared brain-dead patient whose organs are being removed for donor purposes

9. STUDY ENDPOINTS

The study's endpoint is the regional measurement of sulfasalazine, the metabolic breakdown products of sulfasalazine in the digestive tract and peripheral circulation, and the gut microbiota in the digestive tracts of healthy volunteers.

Safety assessments will include the monitoring of subject-reported adverse events as communicated to the study staff.

10. SAFETY

10.1 Definition of Adverse Event

An adverse event (AE) is any untoward, undesirable, unplanned clinical event in the form of signs, symptoms, or clinical significant deviation from baseline in laboratory or physiological observations occurring in a human being participating in a clinical study with a Sponsor study device regardless of a causal relationship to device or device delivery and removal procedures. This includes the following:

- Any clinically significant worsening of a pre-existing condition;
- Any reoccurrence of a pre-existing condition;
- An AE that has been associated with the premature removal of the device.

An adverse device effect (ADE) is any untoward and unintended response to the investigational device or device delivery and removal procedures.

10.2 DEFINITION OF SERIOUS ADVERSE EVENT

A **serious** adverse event (SAE) is any adverse event that suggest a significant hazard or side effect, regardless of the PI's or Sponsor's opinion on the relationship to the investigational product and that results in, but may not be limited to, any of the following outcomes:

- death (regardless of the cause)
- a life-threatening event
- hospitalization or prolongation of existing hospitalization (any inpatient hospital admission that includes a minimum of an overnight stay in a health care facility)
- a persistent or significant disability/incapacity
- a congenital anomaly or birth defect
- significant medical events which requires medical intervention to prevent any of the above outcomes

Significant medical events are those which may not be immediately life-threatening, but may jeopardize the subject and may require intervention to prevent one of the other serious outcomes listed above.

Hospitalization for elective treatment of a pre-study condition that did not worsen while on study and hospitalizations for treatment of non-adverse events (e.g. cosmetic surgery) are not considered serious adverse events.

An **unexpected** adverse medical device event is any adverse event, the specificity or severity of which is not consistent with information in the current Investigator's Brochure (IB) for an unapproved medical device.

A **serious adverse device effect** (SADE) is any ADE that has resulted in any consequences characteristics of a serious adverse event or that might have led to any of these consequences if suitable action had not been taken or intervention had not been made or if circumstances had been less opportune.

10.3 DEFINITION OF RELATIONSHIP TO INVESTIGATIONAL DEVICE AND DEVICE DELIVERY AND REMOVAL PROCEDURES

The PI will document his/her clinical judgment of the causal relationship of the investigational product to the AE. The PI should consider and evaluate alternative causes, such as underlying conditions or other risk factors, as well as the temporal relationship of the event and the study intervention in their assessment of causality. The AE relationship will be defined using the criteria outlined in Table 4.

·					
Relationship Criteria	Definition				
PROBABLY	The adverse event is most likely to be explained by the investigational device or device delivery procedure, rather than the subject's clinical state or other agents/therapies; as the event follows a reasonable temporal sequence from the medical device delivery timepoint and it abates upon removal of the medical device.				
POSSIBLY	The adverse event may be explained by the investigational device or device delivery procedure, or the subject's clinical state or other agents/therapies.				
UNRELATED	The adverse event can be explained by the subject's clinical state or other agents/therapies.				

Table 4: Definition of Adverse Event Relationship Criteria

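### Every subject takes sulfasalazine on a device day, but no adverse-event item or table named in the plan attributes events to the drug, and Table 4's UNRELATED row does not say that the device is ruled out

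*Combined protocol and SAP*

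**What the plan says.** **Exposure.** The synopsis and Sections 2.2 and 5 put two devices alone on Day 1, and one 1,000 mg dose of sulfasalazine with two devices on Day 2. A repeat of the Day 2 procedures on Days 12-19 would again combine drug and devices. Section 2.4.1 names gastric distress, nausea and vomiting among the drug's commonest side effects, and expects side effects to be rare and less serious at this single dose.

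**Causality items.** Section 8.1.1 says: "Information to be collected includes type of event, date of onset, date of resolution, investigator-specified assessment of severity and relationship to device, seriousness". Section 10.3 is headed for the device and its delivery and removal procedures. Its text says "The PI will document his/her clinical judgment of the causal relationship of the investigational product to the AE" and leaves *investigational product* undefined.

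**Table 4 (Section 10.3).** The UNRELATED row makes no mention of the device: "The adverse event can be explained by the subject's clinical state or other agents/therapies". The grade above it, POSSIBLY, puts the device in front of the same two alternative causes and reads as follows: "The adverse event may be explained by the investigational device or device delivery procedure, or the subject's clinical state or other agents/therapies".

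**What counts as device-related.** Section 8.1.1 groups three grades together in its follow-up rule: "within 5 days of the EOS that the PI deems definitely, probably, or possibly related to the device". Section 10.5 uses the same grouping: "Relatedness: definite, probably and possibly) Adverse Effect (SADE".

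**Planned output.** Section 11 plans tables of adverse events and of device-related adverse events, with frequency tables by relationship to the device. Its individual listing gives relationship to the *investigational product*, again undefined.

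**Capture.** Section 8.1.1 records events until "48 hours after the End of Study (EOS), regardless of the relationship of the AE to the CapScan Device". Under Sections 10.2 and 10.5, serious events of any cause go to the sponsor within 24 hours, for a period that runs to 14 days after End of Study.

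**The concern.** Two study exposures, the device and the drug, can each plausibly produce the same gastrointestinal complaints, and they are taken on the same day. The plan asks for a causal judgement on only one of them. Section 3 describes the study as focused partly on the safety of the device, Section 12 says it is meant to demonstrate safety, and device-related events are one of the two items that Section 11 lists for descriptive tables.

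Two things follow. First, no named item allows drug-attributed events to be counted, so the expectation in Section 2.4.1 that drug side effects will be rare cannot be checked from the planned tables. Second, the device-related count depends partly on how the investigator reads two Table 4 rows that share the phrase about other agents or therapies. One of those rows counts as device-related and the other does not.

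**Working it through.** The plan gives no expected adverse-event rate and no calculation behind N = 10, so there is no planned figure to reproduce. The check is of the wording, followed by simple arithmetic on what one grading decision does.

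**Step 1. Does any named item refer to the drug?**

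| Place | What the relationship is to |
|---|---|
| 8.1.1, items collected | device |
| 10.3, heading | device and its delivery and removal procedures |
| 10.3, text | *investigational product*, undefined |
| 10.3, Table 4 | device or its delivery procedure |
| 10.5, reporting rule | device or procedure |
| 11, frequency tables | device |
| 11, listing | *investigational product*, undefined |

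None names sulfasalazine. One judgement is broader. For a serious event found after the observation period, Section 10.5 says that an investigator who "considers the event possibly related to the prior trial, he should contact the sponsor". That is not a drug assessment, and it feeds no planned table.

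**Step 2. Read the two Table 4 rows literally.** Let D = the device or its delivery procedure explains the event, C = clinical state does, and O = other agents or therapies do. Sulfasalazine presumably falls under O, although the plan does not say so.

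- POSSIBLY, as worded: D or C or O.
- UNRELATED, as worded: C or O. There is no condition on D.

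Of the 2 × 2 × 2 = 8 combinations, 6 satisfy UNRELATED, and all 6 also satisfy POSSIBLY. Three of the 6 have no device cause, and three have a device cause together with another. A pure drug reaction (O only) is among the 6.

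With UNRELATED reworded as (C or O) and not D, and POSSIBLY as D and (C or O), 0 of 8 combinations satisfy both. An event explained by the device alone then falls outside both rows, and the higher grades cover it.

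**Step 3. Effect of one grading decision.** Take one subject whose only adverse event is a likely drug reaction. Regrading it changes the proportion of subjects with a device-related event by 1/N. At the N = 10 of Section 12:

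- graded UNRELATED: 0/10 = 0% (exact Clopper-Pearson 95% interval 0 to 30.8%);
- graded POSSIBLY: 1/10 = 10% (0.3 to 44.5%).

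The shift is 1/10 = 10 percentage points. The intervals are illustrative only: Section 11 plans confidence intervals for means, not for event proportions.

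**Step 4. What can timing separate?** An event that starts on Day 1 precedes the planned dose, so the drug cannot have caused it. On Day 2 the onset date named in Section 8.1.1 does not place an event before or after the dose. After the dose, the two Day 2 devices and up to two unexpelled Day 1 devices (2 + 2 = up to 4) may be in transit, so timing alone does not assign a cause.

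**The case against.** The strongest reply is that causality grades are clinical judgements, not logical sets. The scale works by contrast: PROBABLY sets the device above other causes, POSSIBLY admits both, and UNRELATED names other causes only. Under a heading about relationship to the device, the label UNRELATED itself suggests that the device is not responsible. Section 10.3 also asks the investigator to weigh alternative causes and timing. This largely stands. A reader might infer from Step 2 that the device-related count is indeterminate under the plan. The documents do not support that: the intended reading is fairly clear, and the defect is that the row does not state it.

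A reader might also infer that drug reactions go unrecorded. They do not. Events of any cause are recorded to 48 hours after End of Study, serious events are reportable for longer, and Section 11 lists every event individually. With at most ten subjects each can be inspected, and the diary has entries for dose and swallowing times. This reply stands for capture. It does not supply an attribution: a listing that carries no drug judgement cannot show which events the investigator ascribed to the drug.

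Nor do the device-specific reporting rules in Sections 10.5 and 14.5 contradict Sections 10.6, 12.1 and 12.4. Those sections deal respectively with documentation, reports to the review board and the subject's duty to inform. They differ in scope without conflicting.

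Two further cautions stand. The adverse-event forms are not in the documents, and the list in Section 8.1.1 is not worded as exhaustive, so a drug field may already exist. Also, a 1/N shift follows from any regrading in a small study. It shows how sensitive the count is, and does not measure how often the wording would mislead.

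**Conclusion.** The concern holds in two parts. The main part is that no causality item or table named in the plan refers to sulfasalazine, so the planned safety tables cannot separate drug-attributed from device-attributed events after the Day 2 dose. The lesser part is that Table 4 leaves the exclusion of the device unstated in UNRELATED, so a literal reader could grade a likely drug reaction as POSSIBLY, which counts as device-related.

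The size is one subject in ten for each ambiguous event that is a subject's only event: 0/10 against 1/10. How many such events will occur cannot be derived from the documents, and Section 2.4.1 expects few. No decision rule depends on the count, since the statistics are mainly descriptive and the study is not powered. The loss is attribution of post-dose events, not their capture.

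The conclusion assumes that *investigational product* means the device, as the Section 10.3 heading and Table 4 indicate, and that the forms carry no drug item beyond what the protocol names. Confidence is moderate because the forms are not shown. The point should be fixed before data collection, as attribution is hard to reconstruct afterwards.

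**What to change.** 1. Add an assessment of relationship to sulfasalazine to the adverse-event and serious-adverse-event forms. If the forms already have one, name it in Sections 8.1.1 and 10.3.
2. Reword Table 4 so that UNRELATED requires that the device and its procedures are not a plausible contributor, and POSSIBLY requires that they are. Define *investigational product* in Sections 10.3 and 11.
3. In Section 11, tabulate adverse events by relationship to the device and, separately, by relationship to the drug.

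The capture of events within five days of End of Study (synopsis, Sections 2.2 and 8.1.1) is worded for device-related events only. It should be reviewed alongside the new drug item.

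The cost is one form field, a few words in Table 4 and one more table, with no added visit, procedure or subject. The change will not resolve every case. Some same-day events will remain possibly related to both device and drug, but the tables will then show that openly.
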